2.5 Withdrawals

Subjects may discontinue study treatment or withdraw their consent to participate in the study at any time without prejudice. The investigator may withdraw a subject from study treatment or from the study if, in his or her clinical judgment, it is in the best interest of the subject or if the subject cannot comply with the protocol.

In addition, any of the following conditions require discontinuation of the subject from study treatment:

- An AE or intercurrent illness that in the opinion of the investigator warrants the subject's withdrawal from study treatment;
- The investigator believes it is not in the best interest of the subject to continue on study
- Specific conditions described in the Management of Adverse Events Sections 3.3.2 and 3.3.2.1;
- Necessity for treatment with other anticancer treatment prohibited by protocol;
- Sexually active subjects who refuse to use medically accepted barrier methods of contraception (e.g, male condom, female condom) during the course of the study and for 4 months after discontinuation of study treatment;
- Women who become pregnant or are breastfeeding;
- If the subject does not recover from his or her toxicities to tolerable Grade ≤ 2 within 6 weeks, the subject will have study treatment discontinued unless there is unequivocal evidence that the subject is benefitting. In this situation, a subject may be able to restart therapy with a dose reduction upon resolution of the toxicity and with agreement of the principal investigator / MD Anderson IND Office;
- Request by regulatory agencies for termination of treatment of an individual subject or all subjects under the protocol;
- Significant noncompliance with the protocol schedule in the opinion of the investigator;
- The minimum dose of study treatment will be 20 mg once daily (qd). Subjects who cannot tolerate 20 mg qd will have study treatment discontinued;

Proprietary Information of MD Anderson

- Progressive disease (PD) or the subject no longer experiences clinical benefit as determined by the investigator

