3.4 Concomitant Medications and Therapies

3.4.1 Anticancer Therapy

Local intervention is discouraged unless medically unavoidable. Subjects receiving local intervention (e.g., palliative radiation) are allowed to continue to receive study treatment at the investigator's discretion.

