3.4.4 Prohibited or Restricted Therapies

The following therapies are prohibited while the subject is on study:

- Any investigational agent or investigational medical device;
- Any drug or herbal product used specifically for the treatment of ACC ;
- Oral anticoagulation with coumarin agents (e.g., warfarin), direct thrombin inhibitors (e.g., dabigatran), direct factor Xa inhibitor betrixaban, platelet inhibitors (e.g., clopidogrel), and chronic use of aspirin above low dose levels for cardio-protection per local applicable guidelines), until 4 weeks after cabozantinib has been permanently discontinued.
- Any other systemic anticancer treatment (e.g., chemotherapy, immunotherapy, radionuclides) and local anticancer treatment such as surgery, ablation, or embolization.

The following therapies should be avoided if possible, while the subject is on study:

- Palliative external radiation to bone metastasis for bone pain should not be routinely performed while on study but can be considered as a treatment for non-target lesions at the investigator's discretion.
- Erythropoietic stimulating agents (e.g., epoetin alfa and darbepoetin alfa) should not be used based on a report of increased risk of tumor recurrence and/or progression associated with erythropoietin;
- Chronic co-administration of cabozantinib with strong inducers of the CYP3A4 family (e.g., phenytoin, carbamazepine, rifampin, rifabutin, rifapentine, phenobarbital, and St. John's Wort) may significantly decrease cabozantinib concentrations and should be avoided if possible. Selection

Proprietary Information of MD Anderson

of alternate concomitant medications with no or minimal CYP3A4 enzyme induction potential is recommended;

- Caution must be used when discontinuing treatment with a strong CYP3A4 inducer in a subject who has been concurrently receiving a stable dose of cabozantinib, because this could significantly increase the exposure to cabozantinib;

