4 STUDY POPULATION

4.1 Inclusion Criteria

A subject must fully meet all of the following criteria to be eligible for the study:

1. The subject is \geq 18 years old on the day of consent
2. Histological confirmation of ACC based on either: i). Weiss Score of \geq 3 in patients who had earlier surgical resection (*Lin-Weiss-Bisceglia system* will be used for oncocytic ACC) OR ii). biopsy results compatible with ACC in the context of clinical setting highly suggestive of ACC (adrenal mass $>$ 4 cm invading surrounding organs or associated with distant metastases).
3. Locally advanced or metastatic disease not amenable to surgery with curative intent with measurable disease per RECIST 1.1 (9) as determined by the investigator based on an assessment of all known disease sites by computerized tomography (CT) scan or magnetic resonance imaging (MRI) of chest/abdomen/pelvis within 28 days before the first dose of cabozantinib. In patients with IV contrast allergy or borderline renal function, CT without IV contrast or 18 FDG PET CT may be used as clinically indicated
4. Eastern Cooperative Oncology Group (ECOG) performance status of 0-2
5. Recovery to baseline or \leq Grade 1 CTCAE v.4.0 from toxicities related to any prior treatments, unless AE(s) are clinically non-significant and/or stable on supportive therapy
6. Life expectancy of at least 3 months
7. Organ and marrow function and laboratory values as follows within 28 days prior to the first dose of cabozantinib:
 - a. Absolute neutrophil count (ANC) \geq 1500/mm³ without colony stimulating factor support
 - b. Platelets \geq 100,000/mm³
 - c. Hemoglobin \geq 9 g/dL
 - d. Bilirubin \leq 1.5 \times the upper limit of normal (ULN). For subjects with known Gilbert's disease, bilirubin \leq 3.0 mg/dL
 - e. Serum albumin \geq 2.8 g/dL
 - f. Serum creatinine \leq 1.5 \times ULN or creatinine clearance (CrCl) \geq 50 mL/min. For creatinine clearance estimation, the Cockcroft and Gault equation should be used:
Male: CrCl (mL/min) = $(140 - \text{age}) \times \text{wt (kg)} / (\text{serum creatinine} \times 72)$. Female: Multiply above result by 0.85
 - g. Alanine aminotransferase (ALT) and aspartate aminotransferase (AST) \leq 3.0 \times ULN
 - h. No radiologic or clinical evidence of pancreatitis
 - i. Urine protein/creatinine ratio (UPCR) \leq 1
 - j. Serum phosphorus \geq 2.5mg/dL, cCalcium \geq 8mg/dL, magnesium \geq 1.2mg/dL, and potassium \geq 3.0 meq/L (CTCAE V4.03 grade 1 cut off levels).

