5.5 Tumor Assessment

Serial imaging studies will be used to assess measurable disease per RECIST 1.1 criteria (9). Contrast-enhanced computerized tomography (CT) scan or magnetic resonance imaging (MRI) of chest/abdomen/pelvis will be obtained every 8 weeks (+/- 5 days) after the start of study drug administration. In patients with IV contrast allergy or borderline renal function, CT without IV contrast or 18 FDG PET CT may be used as clinically indicated.

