7.3 Sample Size

This is a pilot clinical trial and is not powered for significance in statistical comparison as there is insufficient existing evidence to predict the likely outcomes. The maximum number of subjects to be recruited for the study is 18.

It is expected for the current trial that the drug will achieve a minimum PFS4 of 20% while the maximum toxicity rate should be below 30%. PFS4 is defined as no disease progression or death within the first 4 months of the proposed treatment. If the trial is not terminated early, a posterior 90% credibility interval for the primary endpoint PFS4 rate will have a width of 0.271, given 3 patients achieving PFS4 under the assumption of 20% PFS4 rate.

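### Section 3.4.1 lets patients stay on cabozantinib after any local intervention, against 3.4.4 and 2.5, and the PFS4 definition can then count a locally treated patient as a success

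*Combined protocol and SAP*

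**What the plan says.** Four parts of the combined protocol and SAP bear on this.

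- **Section 3.4.1 (Anticancer Therapy).** "Local intervention is discouraged unless medically unavoidable". The next sentence reads: "Subjects receiving local intervention (e.g., palliative radiation) are allowed to continue to receive study treatment at the investigator's discretion". No type of local intervention is excluded.
- **Section 3.4.4 (Prohibited or Restricted Therapies).** The list of therapies prohibited on study includes "local anticancer treatment such as surgery, ablation, or embolization". A separate list of therapies to avoid if possible covers palliative external radiation to bone metastasis for pain, which "can be considered as a treatment for non-target lesions at the investigator's discretion".
- **Section 2.5 (Withdrawals).** The conditions that require study treatment to stop include "Necessity for treatment with other anticancer treatment prohibited by protocol".
- **Section 7.3 (Sample Size).** "PFS4 is defined as no disease progression or death within the first 4 months of the proposed treatment".

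Section 5.5 sets the imaging schedule and adopts RECIST 1.1. Section 7.4 sets the Bayesian stopping rules on the PFS4 and toxicity counts. Section 7.5 specifies Kaplan-Meier estimation and the timing of the reviews. None of them says in its own text how a patient who receives local treatment before progression is to be scored.

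**The concern.** For an unavoidable ablation, embolization or tumour resection, 3.4.1 leaves continuation to the investigator, while 3.4.4 and 2.5 together require the drug to stop. The medical-necessity condition in 3.4.1 does not reconcile them, because necessity is what triggers the stop in 2.5.

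The contradiction reaches the primary endpoint. A patient who has a lesion removed, ablated or embolized in the first 4 months, and has no documented progression or death by then, meets the 7.3 definition of success. Any benefit of the local treatment would be credited to cabozantinib. The trial is open-label and single-arm, with at most 18 patients, and the futility rule runs on the raw PFS4 count. What is at stake is the PFS4 estimate and the futility decision. There is no efficacy success threshold that could be crossed wrongly.

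**Working it through.** **1. Is there a conflict, and for which treatments?**

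| Local treatment | 3.4.1 | 3.4.4 | 2.5 | Consistent? |
|---|---|---|---|---|
| Palliative radiation, non-target bone lesion | May continue | Tolerated | Not triggered | Yes |
| Surgery, ablation, embolization | May continue (no type excluded) | Prohibited | Drug must stop | No |
| Radiation of a target or non-bone lesion | May continue | Not within the bone exception | Unclear | Unclear |

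**2. Reproduce the plan's figures.** Inputs: prior Beta(0.20, 0.80) for PFS4 and Beta(0.25, 0.75) for toxicity (Section 7.4), maximum n = 18 (Section 7.3), looks at 6, 9, 12 and 15 (Table 7-1).

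- With x successes in n, the PFS4 posterior is Beta(0.20 + x, 0.80 + n − x). For x = 3, n = 18 this is Beta(3.20, 15.80). The equal-tailed 90% interval is 0.053 to 0.324, width 0.271, as Section 7.3 states.
- Applying the two 0.90 cutoffs returns every boundary in Table 7-1.
- Exact enumeration of those boundaries, with PFS4 and toxicity independent, returns all nine rows of Table 7-2. For example, PFS4 0.10 with toxicity 0.10 gives early stopping 0.720 and mean n 10.5; PFS4 0.25 with toxicity 0.10 gives 0.243 and 15.5.

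The design figures are therefore correct. The issue is what is allowed into the count.

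**3. Effect of one patient.** Futility stops if Prob(PFS4 < 0.20 | data) > 0.90.

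| Look | Without the patient as success | With the patient as success |
|---|---|---|
| n = 6 | 0/6: 0.972, stop | 1/6: 0.658, continue |
| n = 12 | 1/12: 0.901, stop | 2/12: 0.671, continue |

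These are the only two points where a futility stop can occur. Passing n = 6 needs at least 1 success, so 0/9 cannot arise; passing n = 12 needs at least 2, so 0/15 and 1/15 cannot arise.

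The chance of 0/6 is (1 − p)^6: 0.90^6 = 0.531 at true PFS4 0.10, and 0.75^6 = 0.178 at 0.25. The chance of stopping at 1/12 (toxicity 0.10) is 0.188 and 0.063 respectively.

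At n = 18, one patient is 1/18 = 5.6 percentage points. Going from 3 to 4 successes moves the 90% interval from 0.053–0.324 to 0.087–0.389.

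**4. Effect on early stopping.** If a share f of true failures is scored as success, the apparent rate is p + (1 − p)f. The documents give no value for f, so the shares below are assumed. True PFS4 0.10, toxicity 0.10:

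| f | Apparent rate | Early stopping |
|---|---|---|
| 0 | 0.100 | 0.720 |
| 1% | 0.10 + 0.90 × 0.01 = 0.109 | 0.685 |
| 2% | 0.10 + 0.90 × 0.02 = 0.118 | 0.649 |
| 1/18 (5.6%) | 0.10 + 0.90/18 = 0.150 | 0.529 |

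**5. Effect of the opposite rule.** If a share s of true successes is scored as failure, the apparent rate is p(1 − s). At PFS4 0.25 and toxicity 0.10, s = 1/18 gives 0.25 × 17/18 = 0.236, and early stopping rises from 0.243 to 0.273. With s = 2/18 the rate is 0.222 and early stopping is 0.307.

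**The case against.** The strongest reply is that the specific provision governs the general one. Section 3.4.1 is two sentences whose only example is palliative radiation; 3.4.4 is where exclusions are listed, and 2.5 makes the stop mandatory. On that reading radiation continues, everything else comes off drug, and only a cross-reference is missing. This is a workable reading, but 3.4.1 does not say it. It also leaves scoring open: a patient taken off drug without progression still has no stated PFS4 status, and Table 5-1 schedules no tumour assessment in its post-treatment column.

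The exposure is narrow, and this stands. Entry requires disease "not amenable to surgery with curative intent". Imaging "will be obtained every 8 weeks (+/- 5 days) after the start of study drug administration", so for a patient kept on drug, progression found later within the 4 months is still a failure. Section 2.5 also stops the drug on loss of clinical benefit, and 3.3.2.7 asks for a 28-day stop before major surgery where possible. Bias needs a patient treated locally within 4 months, unprogressed at that point, who would otherwise have progressed.

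Sections 7.4 and the reporting text after Table 7-2 refer to evaluable patients, without defining the term. A patient removed from treatment might therefore not be counted at all. Success is the literal result of 7.3, not the only possible one.

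Section 7 is also silent on other departures before progression, such as withdrawal or stopping for toxicity. That is true, but here the protocol additionally gives conflicting instructions.

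A reader might infer that the trial's PFS4 will be inflated, or that early stopping will fall to 0.529. The documents do not support either, since the shares are assumed. Nor do they support extending the conflict to palliative radiation of non-target bone lesions, where 3.4.1 and 3.4.4 agree. Whether RECIST 1.1 itself deals with locally treated lesions cannot be settled from these documents; only the absence of a rule in the protocol's own text is established.

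**Conclusion.** The concern holds in a limited form. The text of 3.4.1 conflicts with 3.4.4 and 2.5 for surgery, ablation and embolization, and 7.3 read literally can turn a locally treated patient into a PFS4 success. No stated design figure is wrong.

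The likely size is small and cannot be estimated from the documents. What can be said is conditional: at 0/6 or 1/12, one reclassified patient is enough to turn a futility stop into continuation. If the drug is poor (true PFS4 0.10, toxicity 0.10), the trial reaches one of those two points about 72% of the time (0.531 + 0.188 = 0.719). Over assumed misclassification of 1% to 5.6% of true failures, early stopping falls to between 0.685 and 0.529, from 0.720. These results assume independent endpoints and misclassification that strikes true failures at random. The point deserves correction because it touches the primary count and the remedy is cheap.

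**What to change.** 1. In Section 3.4.1, limit the permission to continue to the palliative radiation of non-target bone lesions that 3.4.4 tolerates, and cross-reference 3.4.4 and 2.5.
2. In Section 7, state that a patient who has surgery, ablation or embolization of a tumour lesion, or any radiation outside the 3.4.4 allowance, within 4 months and before documented progression is not counted as a PFS4 success for Table 7-1. State that patients who have the allowed radiation remain evaluable.
3. List the affected patients, and report PFS4 a second time by RECIST status regardless of local treatment.

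No patients, visits or scans are added. Scoring as non-success is one choice among several; it suits Table 7-1, which needs a yes/no count. Its cost is a possibly lower PFS4 and a slightly higher chance of a futility stop with an active drug: at PFS4 0.25 and toxicity 0.10, early stopping goes from 0.243 to 0.273 if 1/18 of true successes are affected. The same one-patient reversal at 0/6 or 1/12 would then work against the drug. The second analysis makes this visible.

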3.4.2 Other Medications

All concomitant medications used by the subject (including prescription and over-the-counter medications, transfusions, vitamins, herbal remedies, and nutritional supplements) during the period from 28 days before the first dose of study treatment through 30 days after the date of the last dose of study treatment are to be recorded in the medical record.

3.4.3 Allowed Therapies

- Antiemetics and antidiarrheal medications are allowed prophylactically in accordance to standard clinical practice if clinically indicated;
- Granulocyte colony-stimulating factors (G-CSF or GM-CSF) are allowed if used per clinical guidelines (e.g., American Society of Clinical Oncology [ASCO] or [European Society for Medical Oncology] ESMO guidelines);
- Drugs to control hormonal excess symptoms (spironolactone, metyrapone, mifepristone, and ketoconazole). If using strong CYP3A4 inhibitor such as ketoconazole is unavoidable, cabozantinib dose needs to be reduced by 20 mg. Resuming prior dose level can be done 2-3 days after discontinuing ketoconazole.

Proprietary Information of MD Anderson

- Drugs used to control bone loss (e.g., bisphosphonates and denosumab) are allowed if started before screening activities but may not be initiated or exchanged during the course of the study and require principal investigator's approval;
- Transfusions, hormone replacement, and short term higher doses of corticosteroids should be utilized as indicated by standard clinical practice;
 - Individualized anticoagulation therapy with heparin or direct factor Xa inhibitors rivaroxaban, edoxaban, or apixaban is allowed if it can be provided safely and effectively under the following circumstances:
 - At the time of first dose of study treatment:
 - Low dose low molecular weight heparins (LMWH) for prophylactic use are allowed if clinically indicated and the benefit outweighs the risk per the Investigator's discretion.
 - Therapeutic doses of LMWH or the direct factor Xa inhibitors rivaroxaban, edoxaban, or apixaban are allowed if the subject has no evidence of brain metastasis, has been on a stable dose of the anticoagulant for at least 1 week, and has had no clinically significant hemorrhagic complications from the anticoagulation regimen or the tumor. See Section 3.4.4 for prohibited anticoagulants.
 - After first dose of study treatment:
 - Low dose low molecular weight heparins (LMWH) for prophylactic use are allowed if clinically indicated and the benefit outweighs the risk per the Investigator's discretion.
 - Therapeutic doses of LMWH or the direct factor Xa oral inhibitors rivaroxaban, edoxaban, or apixaban are allowed if clinically indicated (e.g., for the treatment of DVT), and the benefit outweighs the risk per the Investigator's discretion. See section 3.3.2.9 for management of thromboembolic complications while on study. See section 3.4.4 for prohibited anticoagulants.
 - Accepted clinical guidelines regarding appropriate management while receiving any kind of anticoagulation therapy must be followed. This includes, but is not limited to, subject education regarding the potential adverse drug reactions,

Proprietary Information of MD Anderson

monitoring laboratory parameters, dose adjustments (e.g., due to kidney dysfunction). Caution is warranted in settings associated with an increased risk for bleeding such as gastrointestinal cancers, urothelial cancers, gastrointestinal mucosal abnormality (e.g., mucositis), renal or hepatic impairment, thrombocytopenia, arterial hypertension, or prior history of gastrointestinal bleed. For direct factor Xa inhibitors, the potential for drug-drug interaction with other concomitant medications, as well as gastrointestinal absorption, should be considered. Aspirin and other nonsteroidal anti-inflammatory drugs (NSAIDs) should not be used concomitantly with heparin or factor Xa inhibitors due to the increased risk for bleeding complications. The risks and benefits of the use of anticoagulants should be reassessed on a regular basis. For more information regarding the use of anticoagulants, refer to the prescribing information of the anticoagulant and accepted clinical practice guidelines.

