3.3.2.11 Corrected QTc Prolongation

The effect of orally administered cabozantinib 140 mg qd on QTc interval was evaluated in a placebo-controlled study in subjects with MTC. A mean increase in QTcF of 10-15 ms was observed after 4 weeks after initiating cabozantinib treatment. A concentration-QTc relationship could not be definitively established. Changes in cardiac wave form morphology or new rhythms were not observed. No cabozantinib-treated subjects in this study had a QTcF $> 500 \text{ ms}$.

Unless otherwise specified in certain protocols, only subjects with a baseline QTcF $\leq 500 \text{ msec}$ are eligible for cabozantinib research studies. Cabozantinib should be used with caution in subjects with QT prolongation risk, a history of QT interval prolongation, or who are taking antiarrhythmics or drugs

Proprietary Information of MD Anderson

known to prolong the QT interval. Concomitant treatment with strong CYP3A4 inhibitors, which may increase cabozantinib plasma concentrations, should be avoided.

If at any time on study there is an increase in QTcF to an absolute value > 500 ms or an increase of > 60 ms above baseline, two additional ECGs must be performed with intervals not less than 3 min apart within 30 min after the initial ECG.

If the average QTcF from the three ECGs is > 500 ms or increased by > 60 ms above baseline, the following actions must be taken:

- Withhold study treatment
- Immediately notify the MD Anderson IND Office
- Hospitalize symptomatic subjects (e.g., with palpitations, dizziness, syncope, orthostatic hypotension, a significant ventricular arrhythmia on ECG) for a thorough cardiology evaluation and management
- Consider cardiology consultation for asymptomatic subjects for evaluation and management
- Check electrolytes, especially magnesium, potassium and calcium; correct abnormalities as clinically indicated
- Check concomitant medications for any medication that may have contributed to QT prolongation, and if possible, discontinue these medications (<http://www.qtdrugs.org>)
- Repeat ECG triplices hourly until the average QTcF is ≤ 500 msec, or otherwise determined by consultation with a cardiologist or appropriate expert.

Subjects with QTc prolongation and symptoms must be monitored closely until the QTc elevation and symptoms have resolved. Study treatment may be restarted at a reduced dose level if all of the following conditions are met:

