- Co-administration of cabozantinib with strong inhibitors of the CYP3A4 family (e.g., itraconazole, clarithromycin, indinavir, nefazodone, nelfinavir, and ritonavir) may increase cabozantinib concentrations and is not permitted. Grapefruit and Seville oranges may also increase plasma concentrations of cabozantinib and should be avoided. Ketoconazole use will be permitted to treat Cushing syndrome if clinically unavoidable. Cabozantinib dose needs to be reduced by 20 mg when using ketoconazole. Resuming prior dose level is permitted 2-3 days after discontinuing ketoconazole.

Additional information on potential drug interactions with cabozantinib is provided in Section 3.4.5.

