3.4.5 Potential Drug Interactions

Cytochrome P450 (CYP): Data from a clinical drug interaction study (Study XL184-008) show that clinically relevant steady-state concentrations of cabozantinib appear to have no marked effect on the area under the plasma drug concentration time curve (AUC) of co-administered rosiglitazone, a CYP2C8 substrate. Therefore, cabozantinib is not anticipated to markedly inhibit CYP2C8 in the clinic, and by inference, is not anticipated to markedly inhibit other CYP450 isozymes that have lower [I]/Ki values compared with CYP2C8 (i.e., CYP2C9, CYP2C19, CYP2D6, CYP1A2, and CYP3A4). In vitro data indicate that cabozantinib is unlikely to induce cytochrome P450 enzymes, except for possible induction of CYP1A1 at high cabozantinib concentrations (30 μ M).

Cabozantinib is a CYP3A4 substrate and a weak substrate for CYP2C9 (but not a CYP2D6, CYP2C8, CYP2C19, CYP2B6, or CYP1A2 substrate), based on data from in vitro studies. Results from a clinical pharmacology study, XL184-006, showed that concurrent administration of cabozantinib with the strong CYP3A4 inducer, rifampin, resulted in an approximately 77% reduction in cabozantinib exposure (AUC values) after a single dose of cabozantinib in healthy volunteers. Chronic co-administration of cabozantinib with strong inducers of the CYP3A4 family (eg, phenytoin, carbamazepine, rifampin, rifabutin, rifapentine, phenobarbital, and St. John's Wort) may significantly decrease cabozantinib concentrations. The chronic use of strong CYP3A4 inducers should be avoided. Other drugs that induce CYP3A4 should be used with caution because these drugs have the potential to decrease exposure (AUC) to cabozantinib. Selection of alternate concomitant medications with no or minimal CYP3A4 enzyme induction potential is recommended.

Results from a clinical pharmacology study, XL184-007, showed that concurrent administration of cabozantinib with the strong CYP3A4 inhibitor, ketoconazole, resulted in a 38% increase in the cabozantinib exposure (AUC values) after a single dose of cabozantinib in healthy volunteers. Co-administration of cabozantinib with strong inhibitors of the CYP3A4 family (eg, ketoconazole, itraconazole, clarithromycin, indinavir, nefazodone, nelfinavir, and ritonavir) may increase cabozantinib concentrations. Grapefruit and Seville oranges may also increase plasma concentrations of cabozantinib and should be avoided. Strong CYP3A4 inhibitors should be avoided and other drugs that inhibit

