4.2 Exclusion Criteria

A subject who meets any of the following criteria is ineligible for the study:

1. Received cytotoxic chemotherapy, radiation therapy, or targeted therapy (including investigational cytotoxic chemotherapy) or biologic agents (e.g., cytokines or antibodies), or other investigational agent within 28 days of study enrollment.
2. For patients who received mitotane within 6 months of consenting, mitotane should have been stopped at least 28 days prior to study enrollment **AND** to have mitotane serum level of < 2 mg/L.
3. Prior treatment with cabozantinib or other cMET inhibitors
4. Known brain metastases or cranial epidural disease unless adequately treated with radiotherapy and/or surgery (including radiosurgery) and stable for at least 4 weeks before the first dose of study treatment. Eligible subjects must be neurologically asymptomatic and without corticosteroid treatment at the time of the start of study treatment.
5. The subject has not recovered to baseline or CTCAE \leq Grade 1 from toxicity due to all prior therapies except alopecia and other non-clinically significant AEs.
6. Prothrombin time (PT)/ International Normalized Ratio (INR) or partial thromboplastin time (PTT) test $\geq 1.3 \times$ the laboratory ULN within 28 days before the first dose of study treatment.
7. Concomitant anticoagulation with coumarin agents (e.g., warfarin), direct thrombin inhibitors (e.g., dabigatran), direct factor Xa inhibitor betrixaban, or platelet inhibitors (e.g., clopidogrel). Allowed anticoagulants are the following:
 - a. Prophylactic use of low-dose aspirin for cardio-protection (per local applicable guidelines) and low-dose low molecular weight heparins (LMWH).
 - b. Therapeutic doses of LMWH or anticoagulation with direct factor Xa inhibitors rivaroxaban, edoxaban, or apixaban in subjects without known brain metastases who are on a stable dose of the anticoagulant for at least 1 week before first dose

Proprietary Information of MD Anderson

of study treatment without clinically significant hemorrhagic complications from the anticoagulation regimen or the tumor.

8. Severe and uncontrolled Cushing syndrome despite medical management (e.g.: systolic blood pressure $>160\text{mmHg}$ or hyperglycemia with fasting glucose above 300mg/dL).
9. The use of strong CYP3A4 inhibitor (with the exception of ketoconazole).

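### For strong CYP3A4 inhibitors other than ketoconazole started during the study, the protocol can be read as allowing, forbidding or merely discouraging use

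*Combined protocol and SAP*

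**What the plan says.** Five sections of the combined protocol and SAP deal with strong CYP3A4 inhibitors.

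- **3.4.3 Allowed Therapies**, in the bullet on drugs that control hormone excess: "If using strong CYP3A4 inhibitor such as ketoconazole is unavoidable, cabozantinib dose needs to be reduced by 20 mg". The next sentence lets the prior dose resume 2-3 days after ketoconazole is stopped.
- **3.4.4 Prohibited or Restricted Therapies** has two lists. The first names prohibited therapies, and strong CYP3A4 inhibitors are not in it. The second opens "The following therapies should be avoided if possible, while the subject is on study". One of its bullets gives itraconazole, clarithromycin, indinavir, nefazodone, nelfinavir and ritonavir as examples of strong inhibitors and says that co-administration "may increase cabozantinib concentrations and is not permitted". The same bullet continues "Ketoconazole use will be permitted to treat Cushing syndrome if clinically unavoidable" and "Cabozantinib dose needs to be reduced by 20 mg when using ketoconazole", with the same 2-3 day resumption rule.
- **3.4.5 Potential Drug Interactions** names ketoconazole with the same six drugs as strong inhibitors. It then begins its instruction "Strong CYP3A4 inhibitors should be avoided and other drugs that inhibit" and asks for caution with those other drugs. It does not mention the ketoconazole exception.
- **3.3.2.11 Corrected QTc Prolongation**: "Concomitant treatment with strong CYP3A4 inhibitors, which may increase cabozantinib plasma concentrations, should be avoided".
- **4.2 Exclusion Criteria, item 9**, bars from entry "The use of strong CYP3A4 inhibitor (with the exception of ketoconazole").

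**The concern.** These are operative instructions on co-medication and on the cabozantinib dose. If they disagree, the handling of a patient who needs such a drug during the study depends on which section is consulted. It would be unclear whether the combination may be given at all and whether the 20 mg reduction applies. The patient's exposure, any toxicity counted under the monitoring rule in section 7.4, and the exploratory pharmacokinetic data would then reflect an unplanned choice between sections.

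**Working it through.** No arithmetic applies, because this is a question of wording. The statements are set side by side, separating ketoconazole from the other strong inhibitors.

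| Place | Other strong inhibitors, started on study | Ketoconazole |
|---|---|---|
| 3.4.3 | If the class wording is taken literally: allowed if unavoidable, with a 20 mg reduction | Allowed if unavoidable, for symptoms of hormone excess; 20 mg reduction; resume after 2-3 days |
| 3.4.4, bullet | Not permitted | Permitted for Cushing syndrome if unavoidable; 20 mg reduction; resume after 2-3 days |
| 3.4.4, heading of the list holding that bullet | Avoid where possible | Same heading |
| 3.4.5 | Avoid | Named in the class to avoid; exception not repeated |
| 3.3.2.11 | Avoid | Exception not repeated |
| 4.2, item 9 | Bars entry; silent on later use | Exempt at entry; no indication stated |

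**Step 1, other strong inhibitors.** Take a patient already on study who needs clarithromycin.

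- Under 3.4.3, read as class wording, the drug may be given if unavoidable and cabozantinib is reduced by 20 mg. No resumption rule follows, because that sentence names ketoconazole alone.
- Under the 3.4.4 bullet, it may not be given.
- Under the heading over that bullet, and under 3.3.2.11 and 3.4.5, it is discouraged, with no dose instruction if it is given.
- Exclusion 9 does not decide the case, since the patient has already been enrolled.

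The first two readings cannot both hold. The third leaves open both whether the drug may be used and at what cabozantinib dose.

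**Step 2, ketoconazole for Cushing syndrome.** Sections 3.4.3 and 3.4.4 agree on all three elements: use only if unavoidable, a 20 mg reduction, and resumption after 2-3 days. Exclusion 9 is compatible with both. Advice to avoid a drug is also compatible with allowing it when it cannot be avoided. There is one operative rule.

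**Step 3, ketoconazole for other hormone excess.** Section 3.4.3 covers it. The permission in 3.4.4 mentions Cushing syndrome and is silent on the rest. The case is foreseeable, because the adrenal profile in section 5.4 includes aldosterone, DHEA-sulfate, testosterone and estradiol as well as cortisol. This is a difference in breadth, not an opposite instruction.

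**The case against.** The strongest reply is that 3.4.3 was meant for ketoconazole alone. Its sentence sits in a bullet listing four drugs for hormone excess. Ketoconazole is the only one of the four that the protocol itself names as a strong inhibitor, and the next sentence covers resumption after ketoconazole only. On that reading 3.4.3 says nothing about clarithromycin, and the 3.4.4 bullet governs. This is a fair reading and may well be the intended one. But the sentence offers ketoconazole as an example of a class, so the wider reading is open on its face, and no text closes it.

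A second reply is that the misplaced bullet is editorial. The same list also says that erythropoietic agents should not be used, which is likewise stronger than its heading. That is true, but it shows that the headings in 3.4.4 cannot be relied on to tell a prohibition from a restriction.

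A third reply is that this is a single-institution study, and that section 5.6 requires the institution's investigator to approve dose changes made outside. That limits divergence in practice. The approving investigator still works from the same text.

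Some stronger readings are tempting but unsupported:

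- **That ketoconazole itself is subject to three rules.** Step 2 shows that it is not.
- **That 3.4.4 confines ketoconazole to Cushing syndrome.** It grants permission for that use and does not say that no other is allowed.
- **That exclusion 9 permits ketoconazole for any purpose.** It is an entry criterion, not a prescribing rule for the study period.
- **That the conflict can be sized from the 38% rise in AUC in 3.4.5.** That figure is for ketoconazole with a single cabozantinib dose in healthy volunteers. Both sections that permit ketoconazole require the reduction, so ketoconazole without a reduction follows from neither. The documents give no AUC figure for the other inhibitors.

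**Conclusion.** The protocol contradicts itself for strong CYP3A4 inhibitors other than ketoconazole that are started on study: 3.4.3 can be read as allowing them with a reduction, the 3.4.4 bullet forbids them, and the 3.4.4 list heading, 3.3.2.11 and 3.4.5 only discourage them. The contradiction between 3.4.3 and 3.4.4 rests on reading the 3.4.3 sentence as class wording. The mismatch between the 3.4.4 bullet and its own heading, and between that bullet and the softer wording of 3.3.2.11 and 3.4.5, does not depend on that reading.

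Two secondary points hold: the permitted use of ketoconazole is wider in 3.4.3 than in 3.4.4, and 3.4.5 does not point to the exception.

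The size cannot be given. The documents do not say how many of at most 18 patients might need such a drug. The sample size, stopping boundaries and operating characteristics are unaffected. The reason to act is that these are instructions bearing on patient safety and should have one meaning.

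**What to change.** Reconcile 3.3.2.11, 3.4.3, 3.4.4, 3.4.5 and exclusion 9 into one rule. The revised text should:

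- state whether strong inhibitors other than ketoconazole, if needed after enrolment, are prohibited or conditionally allowed;
- state which inhibitors the dose-reduction and resumption sentences cover;
- give the same ketoconazole indications in 3.4.3 and 3.4.4;
- place the 3.4.4 bullet under the heading that matches its content;
- add a cross-reference from 3.4.5 to the ketoconazole exception.

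Which rule stands is for the sponsor to decide. The cost is a wording amendment, submitted under section 12. It needs no new data, assessments or statistical work.
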